11.3 Analysis Methodology for the Primary Endpoint

11.3.1 Primary Analysis of the Primary Endpoint

The primary efficacy analysis will compare the time to relapse in the Double-Blind Treatment Period between vortioxetine and placebo treated patients. Relapse will be defined as either a

total score ≥ 40 on the CDRS-R with a history of 2 weeks of clinical deterioration, or clinical deterioration as judged by the clinician and documented in the eCRF.

The time to relapse is defined as the number of days from the start of the Double-Blind Treatment Period (Randomization visit) to the date of relapse. This will be calculated as follows:

$(\text{Date of relapse} - \text{Date of start of Double-Blind Treatment Period})$

Patients who do not relapse before the end of the Double-Blind Treatment Period (26 weeks) will be censored at week 26. Patients who withdraw from the study for other reason(s) than relapse will be censored at the time of withdrawal.

The two treatment groups will be compared using a Cox regression model with exact adjustment for ties.

Cox Regression Model

The time to relapse will be analysed using a Cox regression model that includes treatment as a fixed factor, and the randomization CDRS-R total score as covariate, and stratifying by inclusion source to allow for different baseline hazards for each inclusion group.

The hazard ratio for vortioxetine compared to placebo will be estimated from the model and presented with p-values and 95% CIs.

In case of non-convergence of the Cox regression model the strata will be grouped in a new stratum variable, and this variable will be defined at the classification meeting based on blinded treatment and relapses from the different enrolment sources.

A one-sided 5% alpha level of confidence will be used.

11.3.2 Sensitivity Analyses of the Primary Endpoint

The following sensitivity analyses will be performed:

1. The primary analysis will be repeated ignoring relapses occurring during the first week, two weeks and four weeks of the Double-Blind Treatment Period, respectively.

For the purpose of this sensitivity analysis 3 subsets of data will be defined:

- i) A subset excluding all patients with a relapse within the first 7 days after the start of the Double-Blind Treatment Period.
- ii) A subset excluding all patients with a relapse within the first 14 days after the start of the Double-Blind Treatment Period.
- iii) A subset excluding all patients with a relapse within the first 28 days after the start of the Double-Blind Treatment Period.

The primary analysis of the study, as described, will be repeated in each of the 3 subsets above and for each subset the hazard ratio for vortioxetine compared to placebo will be estimated from the model and presented with p-values and 95% CIs.

2. The primary analysis will be repeated for the *de novo* patients and for the (pooled) 12709A patients and 12712A patients additionally.

The hazard ratio's for vortioxetine compared to placebo will be estimated from the model and presented with p-values and 95% CIs for *de novo* and rollover patients (pooled 12709A and 12712A) separately.

On an exploratory basis, if feasible, the impact of the use of psychotherapy, severity of illness, gender and age may be investigated. Therefore, these may be added as fixed factors or covariates to the Cox regression model, or subgroups may be created.

11.4 Analysis Methodology for the Secondary Endpoints

11.4.1 Analysis of the Secondary Endpoint(s)

Relapse

The number of relapses will be summarized per visit, per treatment group and overall. The relapse criteria as defined in section 11.3 will be used.

The relapse over the 26 weeks Double-Blind Treatment Period will be analysed using logistic regression, with treatment and inclusion source as fixed factors and CDRS-R Total Score at randomization as covariate. In addition, the analysis will be repeated using the LOCF (Last Observation Carried Forward) approach for missing data.

The odds ratio estimates with 95% confidence intervals will be presented. The odds ratio and the confidence limits will be based on the profile likelihood.

Secondary efficacy variables (CDRS-R total score, PQ-LES-Q scores (total score and overall score), CGI-S and CGI-I) will be analysed on an exploratory basis over the 26-week Double-Blind Treatment Period by Mixed Model Repeated Measurements (MMRM) and analysis of covariance (ANCOVA).

For the purpose of the analysis the change from randomization in CDRS-R total score, PQ-LES-Q scores, and in CGI-S score will be computed.

For both the MMRM and the ANCOVA, the dependent variable will be the change from randomization in CDRS-R total score, change from randomization in PQ-LES-Q scores, change from Randomization in CGI-S score and the absolute CGI-I score, respectively.

The MMRM will have treatment, week and inclusion source as fixed factors and the randomization score will be added as a covariate. For CGI-I, the score at randomization for the CGI-S will be used as covariate.

In addition, the interaction between treatment and week and between randomization score and week will be included and an unstructured covariance matrix will be applied. The Kenward-Roger approximation will be used to estimate denominator degrees of freedom.

In the ANCOVA treatment and inclusion source will be included as fixed factors and the respective randomization score will be included as a covariate. For CGI-I, the score at randomization for the CGI-S will be used as covariate.

Only the observed cases (OC) approach will be used.

Paediatric Quality of Life Enjoyment and Satisfaction Questionnaire

The PQ-LES-Q consist of 15 items, item 1 to 14 assess the degree of satisfaction experienced by patients in various areas of daily functioning and item 15 allows patients to summarize their experience in a global rating.

Each item is rated on a 5-point scale from 1 (*very poor*) to 5 (*very good*). The total score range of item 1 to 14 is 14 to 70, with higher scores indicating greater satisfaction. It takes 5 to 10 minutes to complete the scale.

The same analysis as for item 1-14 will be applied on the global rating (item 15).

Summary statistics on total score (items 1 -14) and the overall score (item 15) will be presented for each visit, per treatment group and overall.

Children depression rating scale revised version (CDRS-R)

The CDRS-R is a clinician-rated scale to measure the severity of depression of children and adolescents. The CDRS-R is rated by a clinician following interviews with the child and parent(s) and consists of 17 items: 14 items rate verbal observations, and 3 items rate non-verbal observations (tempo of language, hypoactivity, and nonverbal expression of depressed affect). Items are rated for severity on a 7-point scale (1 to 7) for 14 items, and on a 5-point scale (1 to 5) for 3 items (sleep disturbance, appetite disturbance, and listless speech). The total score ranges from 17 (normal) to 113 (severe depression).

Summary statistics on total score and all items scores will be presented for each visit, per treatment group and overall.

Clinical Global Impression

The CGI is a clinician rated scale that consist of two subscales: severity of illness (CGI-S) and global improvement (CGI-I).

CGI-S

The CGI-S provides the clinician's impression of the patient's current state of mental illness. The clinician uses his or her clinical experience of this patient population to rate the severity of the patient's current mental illness on a 7-point scale ranging from 1 (Normal - not at all ill) to 7 (among the most extremely ill patients).

CGI-I

The CGI-I provides the clinician's impression of the patient's improvement (or worsening). The clinician assesses the patient's condition relative to randomization on a 7-point scale ranging from 1 (very much improved) to 7 (very much worse).

For both the CGI-S as the CGI-I descriptive statistics as well as frequency counts and percentages will be given for each time point per treatment group and overall.

11.5 Analysis of the Exploratory Endpoints

No formal exploratory endpoints have been defined.

On an exploratory basis, severity of illness, gender and age may be assessed as covariates or to generate subgroups for the Cox regression model as described in section 11.3.1.1. In addition, descriptive statistics will be used to compare patient populations and treatment outcome between the geographical regions.

Also on an exploratory basis, the primary analysis of the study will be repeated for each of the two definitions of relapse below and the hazard ratio for vortioxetine compared to placebo will be estimated from the model and presented with p-values and 95% CIs:

- i) Relapse based on investigator judgement.
- ii) Relapse defined as CDRS-R total score ≥ 40 with 2 weeks of clinical deterioration

11.6 Pharmacokinetic Analyses

The pharmacokinetic analyses will be described in a separate population PK analysis plan.

12 Safety

The safety analyses will be performed for each period, based on the APES and the APRS. Unless otherwise specified the tables and listings of the Open Label Period are based on APES. The tables and listings of the Double-Blind Treatment Period are based on the APRS.

All safety endpoints will be reported for the 12-week Open Label Period and the 26-week Double-Blind Treatment Period separately. The results of the safety analysis of the Open Label Period will be presented by patient group (*de novo* patients and rollover patients from Study 12709A) and overall.

The results of the safety analyses of the Double-Blind Treatment Period will be displayed by treatment group and overall.

12.1 Adverse Events

12.1.1 General Methodology for Adverse Events

Tables by preferred term and tables by system organ class (SOC) and preferred term will be sorted in descending order based on the percentages of patients in the total column.

Unless otherwise specified, the summaries of adverse events will include the total number and percentage of patients with an adverse event and the total number of AEs.

In summaries of adverse events presented by intensity, the maximum intensity of the adverse event will be used for patients who have more than one intensity of that event. Adverse events for which information on intensity is missing will be classified as *severe*.

Listings of adverse events will be sorted by site, patient screening number, and adverse event start date, and include period, preferred term, investigator term, adverse event start date, days since first dose of IMP, dose at onset of AE, duration of the adverse event, action taken, causality, intensity, seriousness, and outcome. For adverse events that change in intensity, each intensity will be included.

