1.1.3.1 Pharmacokinetics

In adults, vortioxetine has shown to be a compound with slow absorption, large volume of distribution and medium clearance. Vortioxetine is slowly, but well absorbed after oral administration and the peak plasma concentration is reached within 7 to 11 hours. Following multiple dosing of 5, 10, or 20 mg/day, mean maximum observed concentration (C_{max}) values of 9 to 33 ng/mL were observed. The absolute bioavailability is 75%. No effect of food on the pharmacokinetics was observed. The mean volume of distribution (V_{ss}) is 2,600 L, indicating extensive extravascular distribution. Vortioxetine is highly bound to plasma proteins (98 to 99%) and the binding appears to be independent of vortioxetine plasma concentrations.

Vortioxetine is extensively metabolised in the liver, primarily through oxidation catalysed by CYP2D6 and to a minor extent CYP3A4/5 and CYP2C9, and subsequent glucuronic acid conjugation. No inhibitory or inducing effect of vortioxetine was observed in the drug-drug interaction studies for the CYP isozymes CYP1A2, CYP2A6, CYP2B6, CYP2C8, CYP2C9, CYP2C19, CYP2D6, CYP2E1, or CYP3A4/5. Vortioxetine is a poor P-gp substrate and

inhibitor. The major metabolite (Lu AA34443) of vortioxetine is pharmacologically inactive. The mean elimination half-life and oral clearance are 66 hours and 33 L/h, respectively. The pharmacokinetics is linear and time independent in the dose range studied (2.5 to 60 mg/day).¹⁵

In the paediatric PK study (12708A), the pharmacokinetic properties of vortioxetine in the children and adolescent population after 14 days of dosing with 5, 10, 15 and 20 mg were investigated. Data showed that the exposures to vortioxetine and its metabolite Lu AA34443, in terms of C_{max} and area under the curve (AUC), increased in a dose-proportional manner and were generally lower in the adolescent patients than in the children, but data suggests that the doses tested (5 to 20 mg/day vortioxetine) and the uptitration scheme employed in this study are appropriate for the paediatric population.

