3.2 Double-Blind Treatment Period

Double-Blind Treatment Period (for all randomized patients)

- Patients who fulfil the randomization criteria and do not meet any of the withdrawal criteria during the Open Label Period or at the time of randomization will be randomly assigned via a centralized randomization system to receive vortioxetine or placebo in a 1:1 ratio. Randomization will be stratified by patient inclusion sources (*de novo* patients, rollover patients from 12709A, or from 12712A).
- Patients randomized to vortioxetine will continue on their final dose from the Open Label Period or the dose they had on their last visit in Study 12712A, as applicable.
- The maximum duration of the Double-Blind Treatment Period will be 26 weeks.
- Patients who relapse during the Double-Blind Treatment Period must be withdrawn from the study. The criterion for a relapse is a CDRS-R total score of ≥ 40 with a history of 2 weeks of clinical deterioration, or a clinical deterioration that in the investigator's opinion warrants alteration of treatment to prevent full relapse.

A Safety Follow-up Visit will be performed 4 weeks after withdrawal or completion of the Double-Blind Treatment Period.

Panel 2 Schedule of Study Design

* Patients in remission (CDRS total score ≤ 28) at the two last visits in the Open Label period / Study 12712A OR with an adequate clinical response ($\geq 50\%$ reduction in the CDRS-R total score compared to the baseline score and a CDRS-R total score ≤ 35) at the two last visits in the Open Label period

**Relapse: CDRS-R total score of ≥ 40 with a history of 2 weeks of clinical deterioration, or a clinical deterioration that in the investigator's opinion warrants alteration of treatment to prevent full relapse

4 Definitions

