- concomitant medication continued after first dose of IMP in Open Label Period
- concomitant medication started at or after first dose of IMP in Open Label Period
- concomitant medication continued after first dose of IMP in Double-Blind Treatment Period
- concomitant medication started at or after first dose of IMP in Double-Blind Treatment Period
- concomitant medication started after last dose of IMP in Double-Blind Treatment Period

Concomitant medications started after withdrawal from treatment will be listed separately.

Two sets of tables will be produced; for the Open Label Period tables will be based on the APES and will present the *de novo* patients and 12709A rollover patients separately as well as in total.

For the Double-Blind Treatment Period, tables will be based on the APRS and presented per treatment group as well as overall.

10 Exposure

Exposure and compliance will be calculated per patient and summarized for Open Label Period and Double-Blind Treatment Period separately. For the Open Label Period results will be summarized for *de novo* and 12709A rollover patients separately as well as in total, whereas for the Double-Blind Treatment Period results will be presented per treatment group and overall.

Exposure (days) to IMP, irrespective of missing doses, in each period, will be calculated as:
Date of last IMP intake – Date of first IMP intake in the respective period+ 1
Exposure in weeks will be calculated as: Exposure in days/7

The calculation will include the patient years of exposure (PYE). PYE will be calculated as the sum of the number of days of exposure to IMP for each patient, divided by 365.25 days.

Compliance will be defined as the number of days in which a dose was taken related to the number of days the patient was expected to take IMP as per the protocol.

Compliance in each treatment period will be calculated as:
(the number of days of dose taken / the number of days a dose was planned)*100

Exposure and compliance will be summarized using standard summary statistics. In addition, exposure to IMP will be categorized in the following intervals:

< 1 week
1-2 weeks
3-4 weeks
5-8 weeks
9-10 weeks
11-12 weeks
>12 weeks

for the Open Label Period,
and:

< 1 week
1-2 weeks
3-4 weeks
5-6 weeks
7-10 weeks
11-14 weeks
15-18 weeks
19-22 weeks
23-26 weeks

>26 weeks relative to randomisation for the Double-Blind Treatment Period.

For the Open Label Period an overview of the dosing pattern per patient will be presented.

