12.5.2 General Behavior Inventory (GBI) 10-Item Mania Scale

The GBI 10-item mania scale is a parent- and patient-rated scale designed to screen for manic symptoms in children and adolescents. The ten items are rated on a 4-point scale from 0 (never or hardly ever) to 3 (very often or almost constantly). The total score ranges from 0 to 30, with higher scores indicating greater pathology. Only the parent-rated scale will be used in this study.

Summary statistics on the total score, absolute scores as well as changes from baseline for each visit as well as the latest assessment will be presented per study period and inclusion source (Open Label Period) and treatment group (Double-Blind Treatment Period).

13 Interim Analyses

No interim analyses will be performed.

14 Sample Size Considerations

The calculation of power is based on a log-rank test for the time to relapse at a one-sided 5% level of significance using SAS Proc Power. A sample size of 80 randomized patients (40 patients per treatment group) will provide at least 80% power to find a difference between vortioxetine and placebo as statistically significant, when expecting cumulative relapse rates at 0.42 and 0.69 over 26 weeks, respectively corresponding to a hazard-ratio of 2.15. The assumption of relapse rates (42% and 69% over 6 months for vortioxetine and placebo, respectively) is based on observed rates from a similarly designed relapse-prevention study of fluoxetine in pediatric patients with MDD who had an adequate response after 12 weeks of acute treatment¹.

It is anticipated that approximately 60% of *de novo* patients enrolled into the Open Label Period will qualify for the Double-Blind Treatment Period. To achieve 80 randomized patients, 150 patients are estimated to be enrolled into the study (depending on number and randomization rate of *de novo* and rollover patients).

15 Statistical Software

The statistical software used will be SAS[®], Version 9.4 or later.

16 Details on Data Handling

An LOCF approach will be used for the Double-Blind Treatment Period of the following scales: CDRS-R, PQ-LES-Q, CGI-I and CGI-S.

The LOCF approach will only be used for the total scores (if applicable). The last usable assessment in the Double-Blind Treatment Period (excluding the randomization assessment) will be used to impute missing values for the LOCF. See also section [Section 16.1.3](#) for the handling of missing data related to COVID-19.

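### Double-blind adverse events are tabulated only as crude counts and percentages, although the plan's own relapse rates imply about 31% longer observation on vortioxetine; adding exposure-adjusted rates is a cheap improvement

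*SAP*

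**What the plan says.** - **Relapse ends participation.** SAP 3.2: "Patients who relapse during the Double-Blind Treatment Period must be withdrawn from the study". Under SAP 4.2, a withdrawn child's double-blind period closes at the withdrawal visit. SAP 12.1.4 counts an event as double-blind only if it starts or worsens before that date; later events go to the Safety Follow-up Period.
- **Relapse is expected to differ between arms.** SAP 14 bases power on a difference "when expecting cumulative relapse rates at 0.42 and 0.69 over 26 weeks", for vortioxetine and placebo respectively.
- **Adverse event displays.** SAP 12.1.1 states that "the summaries of adverse events will include the total number and percentage of patients with an adverse event and the total number of AEs". The tables in SAP 12.1.7 (TEAEs), 12.1.9 (SAEs) and 12.1.10 (events leading to withdrawal) follow that default, and SAP 12 shows double-blind results by treatment group. Protocol 16.8.9 likewise plans only summaries by treatment group.
- **Exposure.** SAP 10 derives patient-years of exposure (PYE) and summarises exposure by arm, but no table in SAP 12 uses PYE. Neither document plans exposure-adjusted rates or time-to-first-event summaries.

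**The concern.** The design ties length of observation to the efficacy outcome. If vortioxetine prevents relapse, children on it stay longer and have more time in which to record an adverse event. A percentage of patients, or a count of events, then mixes the event rate with time under observation, and the mixing grows with the drug's efficacy.

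Long-term safety and tolerability is a stated objective. The open-label period has no control arm, so the double-blind period is this study's only placebo-controlled safety evidence. At stake is how that comparison is read; the efficacy conclusion is not affected.

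**Working it through.** **Inputs.** From SAP 14: 40 per arm, relapse 0.42 (vortioxetine) and 0.69 (placebo) over T = 26 weeks, one-sided 5% log-rank test. Assumed: constant relapse hazard, and no withdrawal for other reasons (the documents give no rate; varied below).

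**1. The plan's own figure.** Hazard ratio = ln(1 − 0.69)/ln(1 − 0.42) = 2.150, as stated. Expected relapses = 40 × (0.42 + 0.69) = 44.4. Schoenfeld power = Φ(√44.4/2 × ln 2.15 − 1.645) = 0.817; a simulated log-rank test (20,000 runs) also gives 0.817. The stated power of at least 80% reproduces.

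**2. Observation time.** Weekly hazard λ = −ln(1 − p)/26: 0.02095 (vortioxetine), 0.04505 (placebo). Mean time under observation = p/λ:
- vortioxetine: 0.42/0.02095 = 20.05 weeks; × 40 × 7/365.25 = 15.37 patient-years
- placebo: 0.69/0.04505 = 15.32 weeks; 11.74 patient-years
- ratio 1.309

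**3. Sensitivity of the ratio.**
- Equal other-reason dropout of 10%, 20%, 30%, 40%: 1.30, 1.29, 1.29, 1.28.
- Weibull relapse times with the same 26-week rates, shape 0.5 to 2: 1.47 to 1.18.

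**4. Crude percentages when the true event rate is equal.** Let h = −ln(1 − R)/26, where R is the risk over a full 26 weeks. Expected crude share = h/(h + λ) × (1 − exp(−26(h + λ))).

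| R | Vortioxetine | Placebo | Ratio |
|---|---|---|---|
| 10% | 7.8% | 6.0% | 1.30 |
| 20% | 15.6% | 12.0% | 1.29 |
| 30% | 23.5% | 18.3% | 1.29 |
| 50% | 39.8% | 31.4% | 1.27 |
| 80% | 66.0% | 54.3% | 1.22 |

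For R = 20% this is 40 × 0.1558 = 6.2 against 40 × 0.1203 = 4.8 children. Expected event counts differ by the full 1.31.

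**5. Early-onset events.** If all the event risk falls in the first 1 to 4 weeks, the crude ratio is only 1.01 to 1.05.

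**6. Effect of the rates.** For R = 20%, h = 0.00858 per week, or 44.8 per 100 patient-years.
- First events per patient-year at risk: mean time at risk is (1 − exp(−26(h + λ)))/(h + λ) = 18.15 and 14.02 weeks, or 13.91 and 10.75 patient-years for 40 children. 6.23/13.91 and 4.81/10.75 both give about 44.8 per 100; ratio 1.00.
- Events per PYE: the 1.31 ratio of counts divided by the 1.31 ratio of PYE also gives 1.00.
- For an event confined to the first 4 weeks (20% risk in both arms), crude shares are 19.2% and 18.4%, ratio 1.05. Dividing by total PYE gives 1.046/1.309 = 0.80, a false advantage for vortioxetine.

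**The case against.** **The effect is small in children and no test is planned.** In the 20% example the arms differ by 1.4 children, against a sampling standard deviation of √(40 × 0.1558 × 0.8442 + 40 × 0.1203 × 0.8797) = 3.1. That is fair, and it limits the importance of the point. It does not argue for leaving in a bias whose source is known beforehand.

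**A reader could adjust from planned output.** Event counts and PYE by arm allow a rough division, and the listings carry onset dates. This stands in part. First-event rates would still have to be built from the listings, and those count days from first dose of IMP, which for children entering through the open-label period need not mean days since randomization.

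**Rates are not neutral either.** Step 6 shows the reverse error for early events. Relapse-driven withdrawal may also be informative for events linked to worsening depression, which a rate does not repair. This stands, and it is why rates should sit beside the percentages and not replace them.

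**Two wider readings are tempting and not supported.**
- A reader might extend the 31% to potentially clinically significant (PCS) values. SAP 12.2 also summarises these by visit, among patients with a value at that visit, and detection follows the number of samples. Laboratory tests and ECGs are scheduled after randomization at Week 10 and at Completion/Withdrawal. If every withdrawn child attends that visit, mean samples are 1 + exp(−10λ) = 1.81 against 1.64, ratio 1.11.
- A reader might infer that early placebo-arm events reflect residual drug or its withdrawal. Protocol 1.1.3.1 says "The mean elimination half-life and oral clearance are 66 hours and 33 L/h, respectively", but that is for adults. No half-life for children is given, and the documents report no discontinuation events with vortioxetine.

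**Conclusion.** The point holds as a cheap improvement. On the plan's own relapse rates, with a constant hazard and no other dropout, vortioxetine children are observed about 31% longer. The range is about 18% to 47% over the relapse-time shapes tried, and equal dropout for other reasons changes it little. Crude double-blind percentages would then overstate vortioxetine's relative frequency by roughly 20% to 30% for events arising at a steady, equal rate through the 26 weeks, and event counts by 31%.

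A reader might infer that the planned tables are bound to make vortioxetine look less safe. The documents do not support that: the size depends on when events occur, the artefact nearly vanishes for events confined to the first weeks, and neither document says how onset will be distributed over time. Nor does it follow that the between-arm reading should rest on rates alone.

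**What to change.** In SAP 12.1.7, 12.1.9 and 12.1.10, keep the crude counts and percentages and add by arm, for double-blind TEAEs, SAEs and events leading to withdrawal:
- patients with a first event per patient-year at risk, with time at risk running from first double-blind dose to the earlier of first event and end of the double-blind period;
- events per PYE, using the PYE of SAP 10.

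State in SAP 12.1.1 that the two displays are read together, because the rates assume a roughly constant hazard. A table of double-blind TEAEs by time since randomization (for example early against later) is an optional supplement that would show where that assumption fails. PCS summaries can stay as planned.

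The cost is a few sentences and tables. Onset dates and PYE are already available, so no new data, visits or changes to conduct are needed.
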